3 THEORETICAL FRAMEWORK

Airway assessment and the management of the difficult airway has consistently been a topic of interest in anaesthesia research and in clinical practice guidelines. The SARS-CoV-2 pandemic has caused a significant shift away from face-to-face consultations and towards virtual assessment. This has the potential to impact upon the accuracy of difficult airway prediction and which could ultimately lead to detrimental patient outcomes.

"Optimising the quality of remote airway assessment and exploring whether it correlates with face-to-face assessment" was an area identified as worthy of research in the Association of Anaesthetists COVID-19 airway management guidance^[5].

We theorise that virtual airway assessment can be used as a valid tool to provide comparable results to in-person anaesthetic assessment. We will collect and collate data to establish the reality using quantitative methods, comparing the results using kappa analysis^[11].

Furthermore, we will enquire on the limitations of virtual assessment by using a qualitative, interpretative approach whereby we find meaning from the personal experience and perspectives of the assessors^[12].

Hypotheses:

- Video assessment of the airway will provide comparable results to in-person assessment of the airway for the following measurements:
 - Mallampati score
 - Upper lip bite test
 - Lower jaw protrusion

- Video assessment of the airway will provide discordant results to in-person assessment of the airway for the following measurements:
 - Mouth opening
 - o Thyromental distance
- Technical limitations experienced during the video assessments are likely to have a greater impact on the adequacy of certain airway measurements than others

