4.2 Outcome

The study outcomes are:

- To determine whether remote video assessment of the adult airway is a suitable alternative to in-person anaesthetic assessment
- Formulate recommendations that may help with optimising future remote video airway assessments

5 STUDY DESIGN and METHODS of DATA COLLECTION AND DATA ANALYIS

This is a single centre, method-comparison study that does not involve an intervention, but does involve the gathering and comparison of patient data. Patients that meet the eligibility criteria will be contacted by researchers using their telephone number. The participants will be provided with a participant information sheet via email, and given time to read the information. This will include information on the nature, significance, implications and risks of the trial and the participant will have the right to withdraw from the trial at any time. The researcher will then give the participant the opportunity to ask questions regarding the study. If the participant agrees to take part in the study, they will be sent an electronic consent form for them to record their consent. Consenting patients will be given a unique study identifying number which will be recorded on a password-protected database held on Great Western Hospital's servers.

Data collection

The study design will be a method-comparison study. This will involve the collection of the patient's airway data via two separate methods, and compare the results. Healthcare professionals working

within the pre-operative assessment clinic at Great Western Hospital are already completing remote video assessments of the airway. As part of the study, they will collect additional data on airway assessment tests and anatomical markers. The data collection points used for airway assessment will be based on the current literature evidence base. The meta-analysis published by Roth et al.^[1] identified the following bedside airway assessment tests with an underlying evidence base:

- Modified Mallampati^[7]
- Thyromental distance^[8]
- Mouth opening^[9]
- Upper lip bite test^[10]

The following tests were identified from the British Journal of Anaesthesia review on predicting difficult intubation^[13]:

- Neck movement
- Lower jaw protrusion

The healthcare professional conducting the assessment will also be asked to record any technical problems or limitations that impeded their assessment of the airway.

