The results will be recorded using paper forms designed by the researcher, which will be stored within a locked cabinet on NHS premises until it is entered onto a password-protected database on the hospital's servers. This will happen as soon as possible and the database will only be accessible to the research team. The unique study identifier will be linked to the individuals' personal data on a separate password-protected database held on the hospital's servers.

No video footage or still images will be stored or recorded.

The data will be archived according to the Sponsor's standard operating procedure.

Patients' demographics will be described using frequency and proportion for categorical data and means and standard deviations for continuous data. A comparison between the results of the two airway assessments made by the non-specialist and the anaesthesiologist will be conducted on each of the airway measurements using kappa analysis.

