7.2 Sampling

7.2.1 Size of sample

A sample size calculation has been performed so that the study has a stated probability of detecting a statistically significant kappa coefficient^[11]. We used an a priori calculation with the assumption that a kappa of ≥ 0.7 could be considered good agreement. Assuming that the average proportion of positive ratings on a dichotomous question is 0.7, that the assessors are unbiased, that the two-tailed null value is 0.5, and that the pairwise kappa we wish to detect is 0.7, we would need 173 subjects. To correct for possible systemic biases, we plan to recruit 200 subjects.

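### Kappa, the only planned comparison, weighs a finding missed by video the same as a false alarm, so it cannot by itself support the suitability conclusion

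*Protocol*

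**What the plan says.** Protocol section 5 describes the comparison in one sentence. Its subject is "A comparison between the results of the two airway assessments made by the non-specialist and the anaesthesiologist", and the method is fixed by the statement that this "will be conducted on each of the airway measurements using kappa analysis". Section 3 names the same method ("comparing the results using kappa analysis"). No other statistic for comparing video with in-person findings appears in the protocol.

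Section 4.2 gives the first study outcome as "To determine whether remote video assessment of the adult airway is a suitable alternative to in-person anaesthetic assessment". Section 3 explains why this matters: the move to virtual assessment may "impact upon the accuracy of difficult airway prediction and which could ultimately lead to detrimental patient outcomes".

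The only numerical yardstick for kappa is in section 7.2.1, where the sample size was calculated "with the assumption that a kappa of ≥ 0.7 could be considered good agreement". That section treats the rating as dichotomous with 0.7 of ratings positive. It does not say whether positive means normal or abnormal, or which measurement is meant.

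**The concern.** The two ways in which video can disagree with the anaesthetist have different consequences. If video over-calls, a patient is flagged unnecessarily. If video misses an abnormal finding, the loss of predictive accuracy that section 3 fears goes unseen. Kappa is symmetric in these two errors, so a kappa reported alone does not tell the reader which one occurred or how often. A favourable conclusion under section 4.2 could then be drawn for a measurement on which video overlooks a large share of what the anaesthetist finds.

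Kappa also depends on how common the abnormal finding is. The six measurements in section 5 need not share a prevalence, so the same kappa need not mean the same quality of video assessment for each.

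**Working it through.** **Inputs.** From section 7.2.1: 200 patients, kappa 0.7 as the yardstick, null 0.5, two-tailed, proportion positive 0.7. Assumed, because not given: the prevalence of abnormal findings per measurement (5% to 70% tried), alpha 0.05 and power 80%.

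**1. The plan's own figure.** The protocol says "that the pairwise kappa we wish to detect is 0.7, we would need 173 subjects". For two unbiased raters with proportion positive π, the cell probabilities are π² + π(1−π)κ, 2π(1−π)(1−κ) and (1−π)² + π(1−π)κ. With π = 0.7 and κ = 0.5 they are 0.595, 0.210 and 0.195. Moving to κ = 0.7 changes them by 0.042, −0.084 and 0.042.

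- Sum of squared change over null value: 0.001764/0.595 + 0.007056/0.210 + 0.001764/0.195 = 0.0456
- n = (1.960 + 0.842)²/0.0456 = 172.1, rounded up to 173

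The figure is reproduced and is not in dispute. The formula gives the same n at π = 0.3, so the abnormal share could be 30% or 70%.

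**2. Equal kappa, different errors.** κ = (po − pe)/(1 − pe). Tables are (abnormal on both, missed by video, false alarm, normal on both).

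| Abnormal in person | Table | po | pe | κ | Missed |
|---|---|---|---|---|---|
| 60 of 200 | 38, 22, 0, 140 | 0.890 | 0.624 | 0.707 | 22/60 = 37% |
| 60 of 200 | 60, 0, 28, 112 | 0.860 | 0.524 | 0.706 | 0/60 |
| 20 of 200 | 12, 8, 0, 180 | 0.960 | 0.852 | 0.730 | 8/20 = 40% |
| 20 of 200 | 11, 9, 0, 180 | 0.955 | 0.856 | 0.6875 | 9/20 = 45% |
| 20 of 200 | 20, 0, 15, 165 | 0.925 | 0.760 | 0.6875 | 0/20 |

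Example for the first row: pe = (60 × 38 + 140 × 162)/200² = 0.624, so κ = 0.266/0.376 = 0.707.

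**3. Largest miss rate at κ = 0.70.** With no false alarms, prevalence p and miss rate m, κ = 1 − m/[1 + (1−m)(1−2p)]. Setting κ = 0.70 gives m = 0.6(1−p)/(1.3 − 0.6p):

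- p = 5%: 0.570/1.270 = 44.9%
- p = 10%: 0.540/1.240 = 43.5%
- p = 30%: 0.420/1.120 = 37.5%
- p = 70%: 0.180/0.880 = 20.5%

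**4. Prevalence at fixed accuracy.** Take sensitivity and specificity both 90%, so po = 0.90 throughout. The share positive on video is q = 0.1 + 0.8p, and pe = pq + (1−p)(1−q).

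- p = 5%: pe = 0.824, κ = 0.076/0.176 = 0.43
- p = 10%: pe = 0.756, κ = 0.144/0.244 = 0.59
- p = 30%: pe = 0.564, κ = 0.336/0.436 = 0.77

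**The case against.** **The analysis plan is not shown and may add accuracy measures.** This is fair as far as it goes: supplementary measures are often left to that document. But the protocol itself fixes kappa as the comparison and sets a conclusion about replacement beside it.

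**This is a method-comparison study with no declared reference standard.** This stands in part. Sensitivity here can only mean relative to the in-person reading. It says nothing about actual intubation difficulty. Sections 2.1 and 4.2 do, however, treat the in-person assessment as what video must match, so the direction of disagreement is meaningful.

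**Kappa of 0.7 is not the decision rule.** Correct. It is a sample-size assumption, and section 4.2 states no numerical criterion. The ceilings in step 3 show what that yardstick tolerates, not a pass mark that the protocol has adopted.

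**The examples rest on assumed prevalences.** Correct, and the size of the problem depends on them. A reader might infer that a measurement missing nearly half of abnormal findings would reach 0.7. In the 9-of-20 example kappa is 0.688, which falls short; miss rates of 43% to 45% reach 0.70 only at a prevalence of about 10% or lower.

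**Kappa's fall with rarity can be a proper chance correction.** This stands against one tempting illustration. At 95% raw agreement with equal margins, kappa is 0.88, 0.72 and 0.47 at 30%, 10% and 5% abnormal. A reader might infer that the rare finding would be wrongly called discordant. But sensitivity falls too: 0.275/0.30 = 92%, 0.075/0.10 = 75% and 0.025/0.05 = 50%. Kappa is following a real loss there. The prevalence point therefore has to be shown at fixed sensitivity and specificity, as in step 4.

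**Conclusion.** The concern holds in this form: kappa is the only comparison in the protocol, it cannot separate missed findings from false alarms, and so it cannot alone carry the section 4.2 conclusion. The symmetry holds at any prevalence. Its practical size does not: the miss rate compatible with kappa 0.70 runs from about 45% at 5% abnormal to 20.5% at 70%, assuming no false alarms. At 30%, which is one reading of the planning proportion in section 7.2.1, more than a third of abnormal findings can be missed at a kappa that a measurement with no misses would share.

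Prevalence dependence is a secondary point: at 90% sensitivity and specificity, kappa ranges from 0.43 to 0.77 between 5% and 30% abnormal, so one benchmark does not mean the same for every measurement. A reader might go further and infer that the hypotheses rank the measurements by kappa. The documents do not support that: section 3 classes each measurement separately, and section 5 analyses each one on its own. Nothing here shows that kappa is a wrong choice or that the 173 is wrong.

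**What to change.** In section 5, for each measurement dichotomised at a cut-off declared before analysis (section 7.2.1 already assumes a dichotomous rating), report beside kappa:

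- the proportion of in-person abnormal findings that video missed, and the proportion of in-person normal findings that it over-called, each with an exact 95% confidence interval and described as relative to the in-person reading;
- positive and negative agreement, which need no reference standard and show disagreement in a rare category. They are themselves symmetric in the two errors, so they add to the first item and do not replace it.

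In section 4.2, state that the suitability conclusion will consider the missed proportion as well as kappa.

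The cost is small but not nil. No extra patients or data items are needed, and the results come from the same two-by-two tables. The protocol declares no cut-offs, however, so the team must agree and record them first. Sensitivity will also be imprecise when few patients are abnormal: even 20 of 20 detected has an exact lower limit of 0.025^(1/20), about 83%. That uncertainty should be shown, because a kappa reported alone leaves it out of sight.

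### One unspecified kappa analysis covers all six airway measurements, including two distances with no stated scale or cut-point, so a discordant result for the distances could not be interpreted

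*Protocol*

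**What the plan says.** Section 5 lists six measurements. Modified Mallampati, thyromental distance, mouth opening and the upper lip bite test come from a meta-analysis that "identified the following bedside airway assessment tests with an underlying evidence base". Neck movement and lower jaw protrusion come from a review article. No units, categories or cut-points are given for any of them.

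The analysis of the primary aim is one sentence in section 5: the comparison "will be conducted on each of the airway measurements using kappa analysis". Section 3 names the same method ("comparing the results using kappa analysis"). Neither place says whether kappa is weighted. No other agreement statistic appears, although section 5 does separate categorical from continuous data when it describes demographics.

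Section 3 sets two directional hypotheses. One reads "Video assessment of the airway will provide comparable results to in-person assessment of the airway for the following measurements" and covers Mallampati, upper lip bite and lower jaw protrusion. The other reads "Video assessment of the airway will provide discordant results to in-person assessment of the airway for the following measurements" and covers mouth opening and thyromental distance. Neck movement has no hypothesis.

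The only hint of a scale is in section 7.2.1. The sample size assumes that "the average proportion of positive ratings on a dichotomous question is 0.7" and that "the two-tailed null value is 0.5", with a kappa of 0.7 to be detected and 0.7 or more regarded as good agreement. It does not say which measurement this describes. Nothing defines discordant as a number.

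**The concern.** Kappa measures agreement between categories. If a distance is kept in centimetres and unweighted kappa is applied, two readings that differ by the smallest recording step count as complete disagreement, and kappa falls as the scale gets finer. The two measurements exposed to this are the two for which discordance is predicted, so a low kappa could reflect the statistic and not the video consultation.

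Kappa also gives neither the size nor the direction of an error. Section 4.2 promises recommendations for optimising video assessment. For a distance, such advice depends on whether video reads consistently long or short, which training might correct, or simply reads erratically, which it might not. The study calls itself a method comparison but plans no estimate of either for its two distances.

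A smaller form of the issue affects measurements recorded as ordered classes. There, the choice between unweighted and weighted kappa can decide on which side of 0.7 a result falls.

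**Working it through.** **1. The protocol's own figure.** Inputs from section 7.2.1: proportion positive p = 0.7 (q = 0.3), null kappa 0.5, kappa to detect 0.7, two-tailed. Alpha 0.05 and 80% power are not stated and are assumed here. The goodness-of-fit formula for a binary kappa with two raters is n = (z_α/2 + z_β)² / Σ[(P_i(0.7) − P_i(0.5))² / P_i(0.5)], with cell probabilities P = {p² + pqκ, 2pq(1 − κ), q² + pqκ}.

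- κ = 0.5: 0.595, 0.210, 0.195
- κ = 0.7: 0.637, 0.126, 0.237
- Sum: 0.00296 + 0.03360 + 0.00905 = 0.04561
- n = (1.960 + 0.842)² / 0.04561 = 172.1, rounded up to **173**

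The stated figure reproduces exactly, for a two-category item only. At 200 subjects the same formula gives about 86% power.

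**2. Distances kept in units.** Simulation with assumed true values N(7.5, 1.0) cm, independent error SD 0.3 cm per method, and no bias. The correlation between methods is 1.0² / (1.0² + 0.3²) = 0.917. Before rounding, the SD of the differences is 0.3 × √2 = 0.42 cm, so the limits of agreement are ±1.96 × 0.42 = ±0.83 cm.

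| Recorded to | Unweighted kappa | Quadratic-weighted kappa |
|---|---|---|
| 0.1 cm | 0.07 | 0.92 |
| 0.5 cm | 0.33 | 0.90 |
| 1 cm | 0.55 | 0.85 |

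Range over other assumptions (SD 1.0 or 0.7 cm, intraclass correlation 0.80 to 0.95): unweighted kappa is 0.04 to 0.14 at 0.1 cm, 0.19 to 0.56 at 0.5 cm, and 0.35 to 0.72 at 1 cm.

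**3. The same distances dichotomised.** At correlation 0.917, kappa is 0.65 with 5% of patients below the cut, 0.72 with 20%, 0.73 with 30% and 0.74 with 50%. Over intraclass correlations 0.80 to 0.95 the range is 0.47 to 0.80.

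**4. Offset against scatter.** A cut at 6.5 cm is used purely for illustration and is not a clinical proposal. In-person error SD is 0.3 cm in both cases.

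| Video error | Kappa at the cut | Mean difference | Limits around it |
|---|---|---|---|
| Reads 0.5 cm long, error SD 0.3 cm | 0.53 | 0.5 cm | ±1.96 × √(0.09 + 0.09) = ±0.83 cm |
| Unbiased, error SD 0.7 cm | 0.53 | 0 | ±1.96 × √(0.09 + 0.49) = ±1.49 cm |

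Kappa is the same for two different faults. The mean difference and limits separate them.

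**5. Ordered classes (supporting only).** Four classes with assumed split 35/35/20/10 and latent correlation 0.85 give kappa 0.47 unweighted, 0.63 linear-weighted and 0.77 quadratic-weighted, with 95% of disagreements one class apart. At latent correlation 0.90, over three assumed splits, unweighted kappa is 0.53 to 0.58 and quadratic-weighted 0.81 to 0.84.

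**6. Precision of the alternative.** The 95% interval around each limit of agreement is about ±1.96 × √(3/n) SDs of the differences: ±0.24 at n = 200 and ±0.26 at n = 173.

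**The case against.** A reader might infer that the choice of kappa by itself confirms the discordance hypothesis. The protocol does not support that. The inference needs distances kept in fine units and unweighted kappa, and the protocol states neither. The data forms are not shown, and the sample size wording points towards two-category ratings. Step 3 shows that dichotomised distances can reach 0.7 or more with the same measurement error. This part of the objection stands.

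It can also be said that cut-points and weighting belong in a statistical analysis plan, which may exist. For ordered classes that is fair: weighting is a choice within kappa analysis, and the ordering of the classes is general knowledge, not something the protocol states. That part is therefore only supporting. For the distances the argument is weaker. Section 5 does not leave the statistic open but fixes kappa for every measurement, so an analysis plan that relied on limits of agreement for the distances would depart from it. The dichotomous assumption in section 7.2.1 is tied to no measurement and no cut-point.

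Finally, limits of about ±0.8 cm are not shown to be clinically acceptable, because the protocol gives no acceptable difference. That is correct, and nothing here claims that video is accurate enough. If values in units are collected, bias and limits could be calculated later, but the protocol does not commit to collecting them.

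**Conclusion.** The concern holds in a limited form. The protocol applies one unspecified kappa to two distances without a recording scale or cut-point, and links neither to the two-category item behind its sample size. Under the assumed errors, one set of unbiased readings gives kappa anywhere from 0.07 to 0.74, depending only on how it is recorded and cut. A discordant result for the distances therefore could not be told apart from an artefact of scale and kappa version, and the hypothesis is not fairly testable as written. Dichotomising removes the forced low value but not the second problem: a 0.5 cm offset and pure extra scatter both gave 0.53.

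The SDs, correlations, class splits and illustrative cut are assumptions, since the protocol gives none. The exact kappas move with them, but the dependence on recording scale does not go away. The figure of 173 is sound for a binary item with 70% positive ratings and is not in dispute.

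**What to change.** Replace the kappa sentence in section 5 with a method for each scale, and make section 3 agree:

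- State the recording scale of each of the six measurements.
- For thyromental distance and mouth opening, record the measured value on both forms. Report the mean difference and 95% limits of agreement, with confidence intervals, against an acceptable difference that the team fixes in advance. Add kappa at one pre-declared cut-point, so that the binary-kappa sample size in section 7.2.1 still applies.
- For ordered classes, pre-specify one weighted kappa and also show exact agreement.
- Use unweighted kappa for two-category items.
- Define comparable and discordant numerically for each measurement.

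This has to be done before recruitment. Section 5 says no video or still images are kept, so a distance recorded only as a category cannot be measured again.

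The cost is protocol wording and a measured-value field on both forms. The sample stays at 200. The real work is agreeing the acceptable difference, the cut-point and one weighting scheme in advance. The weighting needs a stated reason, because in step 5 linear and quadratic weights fell on opposite sides of 0.7.

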6 STUDY SETTING

The study will take place at Great Western Hospital, Swindon, and is a single centre study.

Participants will be identified via the Great Western Hospital Pre-Operative Assessment Clinic. Potential participants will be contacted by the researcher via telephone prior to their attendance at the pre-operative clinic in-order to provide the participant information (via email), check eligibility criteria and gain electronic consent using the Microsoft Forms online platform. Microsoft forms is compliant with GDPR and the Data Protection Act (2018). The consent forms will be password protected, with access granted on an individual basis to select members of the research team.

Prior to recruitment start, staff will undergo the relevant training and receive the necessary information, either remotely, or face-to-face. Pre-operative assessment staff already perform remote video airway assessments as part of their day-to-day job. Data will be collected in the pre-operative assessment clinic and in the operating theatre for the remote video assessment and the in-person assessment respectively. Both data sets will initially be recorded onto paper forms and then transcribed to a secure database, as outlined in section 5. Any paper forms will immediately be disposed of in-keeping with the hospital confidential waste policy.

Participants will be considered eligible for enrolment into this study if they fulfil all of the inclusion criteria and none of the exclusion criteria as defined in section 7.

Using Great Western Hospital is an appropriate setting for this study as it already has an operational video-calling system in place that adheres to the principles of GDPR and meets the necessary data security standards. The hospital also has a research and innovation department that is willing to review the study protocol and support the study through local feasibility approval processes.

